### **10.3.3. Safety Monitoring**

The Lilly CRP will monitor safety data throughout the course of the study.

Lilly will review SAEs within time frames mandated by company procedures. The Lilly CRP will, as is appropriate, consult with the functionally independent Global Patient Safety therapeutic area physician or clinical scientist and will review:

- trends in safety data
- laboratory analytes
- AEs
- If a patient experiences elevated ALT >5x ULN and elevated total bilirubin >2x ULN, clinical and laboratory monitoring should be initiated by the investigator. For patients entering the study with ALT >3x ULN, monitoring should be triggered at ALT >2x baseline.
- Details for hepatic monitoring depend on the severity and persistence of observed laboratory test abnormalities. To ensure patient safety and comply with regulatory guidance, the investigator is to consult with the Lilly CRP regarding collection of specific recommended clinical information and follow-up laboratory tests. See [Attachment 3](#).

For the purpose of this study, in which survival is a primary endpoint, all deaths and SAE reports will be reviewed in a blinded manner by Lilly during the clinical trial. These reports will be reviewed to ensure completeness and accuracy but will not be unblinded to Lilly during the clinical trial. If a death or other clinical AE is deemed serious, unexpected, and possibly related to study drug, only Lilly Global Patient Safety representatives external to the study team will be unblinded for regulatory reporting and safety monitoring purposes. These measures will preserve the integrity of the data collected during this trial and minimize any potential for bias while providing for appropriate safety monitoring.

#### **10.3.4. Complaint Handling**

Lilly collects product complaints on study drugs used in clinical trials in order to ensure the safety of study participants, to monitor quality, and to facilitate process and product improvements.

Complaints related to unblinded comparator drugs or concomitant drugs/drug delivery systems are reported directly to the manufacturers of those drugs/devices in accordance with the package insert.

The investigator or his/her designee is responsible for handling the following aspects of the product complaint process in accordance with the instructions provided for this study:

- recording a complete description of the product complaint reported and any associated AEs using the study-specific complaint forms provided for this purpose
- faxing the completed product complaint form within 24 hours to Lilly or its designee

If the investigator is asked to return the product for investigation, he/she will return a copy of the product complaint form with the product.

### **10.4. Sample Collection and Testing**

[Attachment 1](#) lists the schedule for sample collections and exploratory imaging biomarkers in this study.

[Attachment 2](#) lists the specific tests that will be performed for this study and whether these will be performed at a central or local laboratory.

With the exception of samples for PK testing, all samples should be collected prior to study drug dosing unless otherwise specified in [Attachment 1](#) or [Attachment 5](#). In extenuating circumstances, blood can be drawn up to 3 days before Day 1, but the appropriate central laboratory kit for the respective new visit must be used.

#### **10.4.1. Samples for Study Qualification and Health Monitoring**

Blood, urine, and tissue samples will be collected to determine whether patients meet inclusion/exclusion criteria and to monitor patient health. A serum pregnancy test will be performed (if applicable). Other clinical laboratory tests will be analyzed by central and local laboratories. [Attachment 2](#) lists the specific tests that will be performed for this study. Patient eligibility is based on local laboratory results only, unless the investigator chooses to use the central laboratory for such a purpose. Central laboratory results are used for study report purposes and where appropriate for safety analyses.

At screening, pretreatment formalin-fixed paraffin-embedded (FFPE) tumor tissue will be collected (paraffin blocks or approximately 10 unstained slides cut from that block) for correlation studies of molecular markers and for confirmatory diagnosis. Due diligence should be used to make sure that a tumor specimen (not a normal adjacent or a tumor margin sample) is provided. Pathology notes accompanying archival tissue may also be requested.

Investigators must document their review of each laboratory safety report.

Samples collected for specified laboratory tests will be destroyed within 60 days of receipt of confirmed test results. Tests are run and confirmed promptly whenever scientifically appropriate. When scientific circumstances warrant, it is acceptable to retain samples to batch the tests run or to retain the samples until the end of the study to confirm that the results are valid. Certain samples may be retained for a longer period, if necessary, to comply with applicable laws, regulations, or laboratory certification standards.

#### **10.4.2. Samples for Pharmacodynamics and/or Tailoring Biomarkers**

##### **10.4.2.1. Pharmacogenomic Evaluations**

There is growing evidence that DNA variation may impact a patient's response to therapy. Variable response to therapy may be due to genetic determinants that impact drug absorption, distribution, metabolism, and excretion; the mechanism of action of the drug; the disease etiology; and/or the molecular subtype of the disease being treated. Therefore, where local regulations and ERBs allow, a blood sample will be collected for pharmacogenetic analysis. It is a 1-time collection, as noted in the Study Schedule ([Attachment 1](#)).

It is recommended that the blood sample be taken before study treatment commences but may be taken at any time while the patient is participating in the clinical study. Genes related to safety, efficacy, PK, and/or the mechanism of action of LY2157299 may be tested. Patients will not have the option to request test results and will not receive the genetic test results.

Samples will be stored and analysis may be performed on genetic variants thought to play a role in cancer and targets related to LY2157299 and other administered medicines including genetic changes associated with metabolism and response genes to evaluate their association with observed response to LY2157299.

In the event of an unexpected AE or the observation of unusual response, the samples may be genotyped, and analysis may be performed to evaluate a genetic association with response to LY2157299. These investigations may be limited to a focused-candidate gene study, or, if appropriate, genome-wide association studies may be performed to identify regions of the genome associated with the variability observed in drug response. Samples will only be used for investigations related to disease and drug or class of drugs under study in the context of this clinical program. They will not be used for broad exploratory unspecified disease or population genetic analysis.

The sample will be identified by the patient number (coded) and stored for up to 15 years after the last patient visit for the study at a facility selected by the sponsor. The sample and any data generated from it can only be linked back to the patient by investigator-site personnel. The duration allows the sponsor to respond to regulatory requests related to the study drug.

Samples will be destroyed according to a process consistent with local regulation.

##### **10.4.2.2. Nonpharmacogenetic Biomarker Evaluation and Patient Tailoring**

Collection of samples for measurement of biomarker responses (including E cadherin; TGF-1; platelet factor-4 and T regulatory cell counts; AFP; AFP L3; prothrombin induced by vitamin K

absence [PIVKA II]; urine C-terminal telopeptides of type 1 collagen; immunophenotype; fibrotest; multi-analyte panel [MAP] panel; and other biomarkers related to LY2157299, sorafenib, and HCC) is required for this study. Refer to the Study Schedule ([Attachment 1](#)) for timing of sample collection.

An optional tumor biopsy may be taken by core needle biopsy/surgical biopsy at screening, at Cycle 2, and at the time of disease progression. Due diligence should be used to ensure that a tumor specimen (not a normal adjacent or a tumor margin sample) is provided. Pathology notes accompanying the tissue may also be requested.

The research on stored samples from this study may look at the proteins or other biochemical markers to learn more about compound-specific disease states or how patients respond to or tolerate treatment with LY2157299, sorafenib, or other compounds/medications administered during this study. Stored samples may also be used in validating diagnostic tools or assay(s) related to patient tailoring and disease state.

At baseline, before the patient receives study drug, the following samples will be collected:

- mandatory: pretreatment FFPE tumor tissue (paraffin blocks or approximately 10 unstained slides cut from that block)
- optional tumor biopsy
- plasma

At Cycle 1, the following samples will be collected:

- plasma

At Cycle 2, an optional tumor biopsy will be collected.

At Cycle 2, at each cycle after Cycle 2, and at the time of disease progression, the following samples will be collected:

- plasma

The samples will be coded with the patient number and stored for up to a maximum of 15 years after the last patient visit for the study at a facility selected by the sponsor. The samples and any data generated from them can only be linked back to the patient by investigator site personnel. The duration allows the sponsor to respond to regulatory requests related to the study drug.

Blood, serum, and plasma samples must be collected and shipped according to instructions provided in the central laboratory manual.

Samples will be shipped by the local laboratory to the designated research laboratories, according to the instructions in the central laboratory manual. Designated research laboratories are associated with Lilly and are located in the US and EU.

Samples will be destroyed according to a process consistent with local regulations.

### **10.4.3. Samples for Drug Concentration Measurements Pharmacokinetics**

Sparse samples for PK evaluation will be collected from all patients in the study as indicated in [Attachment 5](#). The actual time of dosing on the day of sampling and the actual time of sampling for each of the samples must be collected. Dose information (dose time and amount of dose) must be collected for the day of sampling and the 2 days prior to the sampling day. This information can be obtained from the patient at the visit for blood sampling.

The sampling times in the schedule are approximate, and the actual sampling time should be recorded. Instructions for the collection and handling of blood samples will be provided by the sponsor.

Plasma PK samples will be collected and analyzed for LY2157299 and sorafenib using a validated method. PK samples for the LY2157299-matched placebo may be collected but will not be analyzed. A maximum of 8 samples may be collected at additional time points during the study if warranted and agreed upon between both the investigator and Lilly.

Drug concentration information will not be reported to investigative sites or blinded personnel.

Bioanalytical samples collected to measure study-drug concentration will be retained for a maximum of 2 years following the last patient visit for the study.

### **10.4.4. Exploratory Imaging Biomarkers for Pharmacodynamic Assessments**

Tumor volume measurements will be performed by the imaging core laboratory for measurable lesions on the CT/MRI scans done for tumor response and will be used to assess the effect of treatments on biological growth rates for each arm.

DCE-MRI and DW-MRI will be performed at clinical sites that have access to an MRI center whose MRI scanner is qualified and approved in advance of patient scanning by the imaging core laboratory designated for this study by the sponsor. Patients who are able to undergo MRI scanning with a gadolinium-based contrast agent (GBCA) will undergo noncontrast DW-MRI and then DCE-MRI in a single scanning session at 2 time points: the first scan at baseline within 10 days of first dose of study drug and the second scan at Cycle 2 Day 22  $\pm$  3 days. The estimated glomerular filtration rate (eGFR) obtained from the creatinine value obtained in Cycle 2 Day 14 will be used to ensure that the patient has maintained an acceptable eGFR for GBCA use in the Cycle 2 Day 22 scan. The metrics obtained from the DCE-MRI scans will include the volume transfer constant between the plasma and the extracellular extravascular leakage space and the initial area under the contrast enhancement curve, typically between 0 seconds and 60 and/or 90 seconds and will be used to compare the antiangiogenic effect across treatment arms. The DW-MRI will typically be obtained for the body areas (abdomen, chest) containing tumor lesions, and the SW-MRI metric(s) that are used to assess the effect of treatment will include the apparent diffusion coefficient obtained across arms.

Details of the imaging acquisitions will be provided in an MRI scanning manual provided by the imaging core laboratory.

### **10.5. Appropriateness of Measurements**

There are no surrogate endpoints used in this study. All efficacy and safety assessments used in this study are standard and appropriate for an oncology study.

## 11. Data Quality Assurance

To ensure accurate, complete, and reliable data, Lilly or its representatives will do the following:

- provide instructional material to the study sites, as appropriate
- sponsor start-up training to instruct the investigators and study coordinators. This session will give instruction on the protocol, the completion of the CRFs, and study procedures.
- make periodic visits to the study site
- be available for consultation and stay in contact with the study site personnel by mail, telephone, and/or fax
- review and evaluate CRF data and use standard computer edits to detect errors in data collection
- conduct a quality review of the database

In addition, Lilly or its representatives will periodically check a sample of the patient data recorded against source documents at the study site. The study may be audited by Lilly or its representatives, and/or regulatory agencies at any time. Investigators will be given notice before an audit occurs.

To ensure the safety of participants in the study and to ensure accurate, complete, and reliable data, the investigator will keep records of laboratory tests, clinical notes, and patient medical records in the patient files as original source documents for the study. If requested, the investigator will provide Lilly, applicable regulatory agencies, and applicable ERBs with direct access to original source documents.

### 11.1. Data Capture System

An electronic data capture system will be used in this trial. The sites will maintain a separate source for the data entered by the site into the sponsor-provided electronic data capture system.

CRF data will be encoded and stored in a clinical trial database. Data managed by a central vendor, such as laboratory test data, ECG data, or CT and MRI images and their analysis results, will be stored electronically in the central vendor's database system. Data will subsequently be transferred from the central vendor to the Lilly generic labs system.

Any data for which the paper documentation provided by the patient will serve as the source document will be identified and documented by each site in that site's study file. Paper documentation provided by the patient may include, for example, a paper diary, PRO measures (for example, a rating scale), a daily dosing schedule, or an event diary.

Data managed by a central vendor, such as laboratory test data or ECG data, will be stored electronically in the central vendor's database system. Data will subsequently be transferred from the central vendor to the Lilly generic labs system.

Data from complaint forms submitted to Lilly will be encoded and stored in the global product complaint management system.

## 12. Sample Size and Statistical Methods

### 12.1. Determination of Sample Size

Approximately 150 patients will be entered into this study in order that 120 patients will be randomly assigned to 1 of 3 treatment arms. The randomization will be in a 1:2:1 allocation ratio with 30 patients in LY2157299 monotherapy, 60 patients in LY2157299 plus sorafenib therapy, and 30 patients in sorafenib plus placebo therapy.

The primary objective is to compare the OS distributions between LY2157299 plus sorafenib therapy (combination arm) with sorafenib plus placebo (control arm) using a Bayesian augmented control design. By incorporating historical information regarding the control group into the Bayesian model, it is possible to improve the operating characteristics compared to a standard (frequentist) analysis. The primary objective will be considered to be met if, after 120 patients have completed at least 2 years of follow-up, the posterior probability is >84% that the HR for OS of the combination arm versus control arm is <1.

The study is designed to observe approximately 100 deaths. Simulations (FACTS version 3.2) were carried out using below assumptions:

- Exponential survival model using summary hazard rates from 2 previous sorafenib trials in Asia-Pacific population (see [Table JBAS.12.1](#)), along with data from the sorafenib plus placebo arm in this study;

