**Clinical Protocol Synopsis: Study H9H-MC-JBAS**

Name of Investigational Product: LY2157299 Monohydrate (hereafter referred to as LY2157299)	
Title of Study: A Randomized Phase 2 Study of LY2157299 versus LY2157299 – Sorafenib Combination versus Sorafenib in Patients with Advanced Hepatocellular Carcinoma	
Number of Planned Patients: Entered: Approximately 150 patients Enrolled/randomly assigned: 120 patients Completed: 100 deaths	Phase of Development: 2
Length of Study: approximately 30 months Planned first patient visit: April 2014 Planned last patient visit: January 2017 Planned interim analyses: #1: approximately 10 patients complete Cycle 1 in LY2157299 monohydrate (hereafter referred to as LY2157299) plus sorafenib arm; #2: 32 patients are randomized and complete 3 cycles of treatment, discontinue from study drug, or die; #3: 70 total deaths	

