**Test Product, Dosage, and Mode of Administration**

LY2157299 will be administered orally by daily dosing morning and evening (twice daily [BID]). The monotherapy dose will be 150 mg BID (300-mg daily dose) for 14 days, followed by 14 days with no study drug. The LY2157299 dose used in combination with sorafenib will be determined based on the results of the H9H-MC-JBAK (JBAK) study Part C (dose will either be 80 mg or 150 mg BID [160 mg or 300 mg daily dose]) for 14 days, followed by 14 days with no study drug.

LY2157299-matched placebo will be administered orally by daily dosing morning and evening (BID) for 14 days, followed by 14 days with no placebo.

Sorafenib will be administered orally by daily dosing morning and evening (BID) at 400 mg per dose (total dosage of 800 mg daily) for 28 days.

One cycle is defined as 28 days in all treatment arms.

**Planned Duration of Treatment Per Patient:** Patients will receive LY2157299 until their disease has progressed, the patient has died, or the patient discontinues for adverse events, investigator's judgment, or other reasons.

**Wash-out period:** none.

**Planned Follow-up Observation Period Per Patient:** Patients who have discontinued study treatment without progression will continue to be followed for progression. Every attempt should be made to gather all information every 2 months (radiological scans and survival), even if a patient starts a new anticancer therapy. All patients will be followed until death. Patients who have entered the treatment extension period will be followed for just 30 days after treatment discontinuation.

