study completion	This study will be considered complete after the final analysis of the primary endpoint (100 deaths) is performed.

SUSARs	suspected unexpected serious adverse reactions
t1/2	half-life
TEAE	treatment-emergent adverse event Any untoward medical occurrence that either occurs or worsens at any time after treatment baseline and that does not necessarily have to have a causal relationship with this treatment.
TGF-β	transforming growth factor beta
TGF-β RI	TGF-β receptor type I
TTP	time-to-tumor progression
ULN	upper limit of normal
US	United States

---

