**Table JBAS.12.1. Summary of Historical Trials**

Trial Name	Sample Size	Median OS (Months)	Hazard Rate (per Week)
Cheng et al. 2009	150	6.5	0.02666
Cheng et al. 2011	410 (Asian Pacific subgroup)	8.8	0.0197
Weighted overall	560	8.2	0.0216

Abbreviation: OS = overall survival.

- A fixed prior distribution for the sorafenib plus placebo hazard rate following a gamma distribution with a mean of 0.0216/week and a weight of 10 (strong prior) and a weight of 1 (weak prior);
- The prior distribution of the log HR between the combination arm and the control arm is assumed to be normally distributed with a mean of 0 and a standard deviation of 100 (weak prior);
- True HRs between the combination arm and the control arm, LY2157299 monotherapy arm and the control arm, are 0.667 and 1, respectively;
- The accrual rate is 10 patients/month (1.7 patients/week);
- The minimum follow-up for the last patient is approximately 2 years (104 weeks).

The simulations indicate that, by randomizing 120 patents, the posterior probability of concluding superiority of the combination arm over the control arm is approximately 83%

(strong prior) and 74% (weak prior) (Table JBAS.12.2). Assuming an HR of 1, the posterior probability of concluding superiority of the combination arm over the control arm (ie, type I error) is approximately 14% to 15%. For comparison purpose, a frequentist analysis using the log-rank test would give a power of 73% assuming the HR = 0.667 and type I error = 14% (one-sided).

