**Table JBAS.12.2. Simulation Results for Final Analysis**

N (Deaths)	Control Rate Prior	Timing of Analysis	Type I Error	Posterior Probability (HR <1) > 0.84
120 (100)	Strong prior for final analysis	FPV + 32.7 months	14%	83%
120 (100)	Weak prior for final analysis	FPV + 32.7 months	15%	74%

Abbreviations: FPV = first patient visit; HR = hazard ratio.

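### The plan gives two different triggers for the final analysis (2 years of follow-up for 120 patients, and 100 deaths), and its accrual rate is converted wrongly

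*Protocol*

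**What the plan says.** **Follow-up trigger.** Protocol 12.1, repeated in SAP 5.2, words the success criterion as "The primary objective will be considered to be met if, after 120 patients have completed at least 2 years of follow-up", the posterior probability of HR < 1 is above 84%. The simulation assumptions in both sections add a minimum of 104 weeks of follow-up for the last patient.

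**Death trigger.** The next paragraph of the same sections says "The study is designed to observe approximately 100 deaths". Protocol Table JBAS.12.2 and SAP Table JBAS.5.2 show N (deaths) as 120 (100) with timing "FPV + 32.7 months". Protocol 4 defines completion: "This study will be considered complete after the final analysis of the primary endpoint (100 deaths) is performed". Protocol 8.1, SAP 5.1 and SAP 6.5 also set completion at 100 deaths.

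**No tie-break.** Protocol 12.2.6 and SAP 6.9.1 restate the 0.84 rule without any timing.

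**Follow-up after the trigger.** Protocol 8.1.1 and SAP 5.1 release off-treatment patients who have completed Visit 801 from long-term follow-up at study completion, unless safety concerns are unresolved. Protocol 10 ends long-term visits at death or once the required deaths are reached. The synopsis says "All patients will be followed until death", and SAP Table JBAS.6.1 agrees with the synopsis.

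**Calendar.** The synopsis gives the study length as "approximately 30 months Planned first patient visit: April 2014 Planned last patient visit: January 2017".

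**Accrual.** Both sample-size sections state 10 patients per month and give 1.7 per week in brackets as its equivalent.

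**The concern.** A single-threshold decision needs one data cut-off. Here the success sentence waits for two years of follow-up, while the completion rules stop the trial and release off-treatment patients at 100 deaths. If the deaths come first, the analysis is run before its own stated condition is met, and routine survival follow-up then ends for the patients who would have completed the two years. This is also a trial in which an internal sponsor committee sees unblinded results at 70 deaths (Protocol 12.2.13), so the final cut-off should not be open to choice.

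The accrual line is a separate arithmetic slip. The two rates are not equivalent, so at most one can have produced the tabulated timings, and the text and tables disagree on when the interims occur.

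**Working it through.** **Inputs** (Protocol 12.1, same in SAP 5.2): 120 patients as 30/60/30; control and monotherapy hazard 0.0216/week; combination hazard 0.667 × 0.0216 = 0.01441/week; exponential survival. Assumed: uniform accrual and no loss to follow-up (none is stated). The two-year condition is read as potential follow-up, that is, 104 weeks after the last patient enters. One month = 365.25/(12 × 7) = 4.348 weeks.

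**1. Accrual conversion.** 10/4.348 = 2.30 per week; 1.7 × 4.348 = 7.39 per month. The historical hazards use a 4-week month (ln 2/(6.5 × 4) = 0.02666), but that gives 10/4 = 2.5 per week, so it does not rescue 1.7.

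**2. Reproducing the plan's timing.** With accrual time A = 120/rate, expected deaths among n patients at week t are n × [1 − (e^(−λ(t−A)) − e^(−λt))/(λA)].

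At 1.7/week, A = 70.6 weeks, and month 32.7 is t = 142.2 weeks:
- control plus monotherapy: 60 × [1 − (0.213 − 0.046)/1.525] = 53.4
- combination: 60 × [1 − (0.356 − 0.129)/1.017] = 46.6
- total: 100.0 deaths, which matches the tabulated 32.7 months.

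The same formula gives 70 deaths at 20.4 months, again as tabulated. Interim 2, taken as the 32nd patient plus 12 weeks, is (32/1.7 + 12)/4.348 = 7.1 months, also as tabulated.

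**3. The two-year trigger.** At 1.7/week, t = 70.6 + 104 = 174.6 weeks = 40.2 months. Expected deaths are 60 × [1 − (0.106 − 0.023)/1.525] + 60 × [1 − (0.224 − 0.081)/1.017] = 56.7 + 51.6 = 108.3.

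| | 1.7/week | 10/month |
|---|---|---|
| Last patient enters (month) | 16.2 | 12.0 |
| 100 deaths (month) | 32.7 | 30.2 |
| Last patient + 104 weeks (month) | 40.2 | 35.9 |
| Expected deaths at that time | 108 | 107 |
| Gap between triggers (months) | 7.5 | 5.7 |
| Last patient's follow-up at 100 deaths (months) | 16.5 | 18.2 |
| Patients enrolled ≥ 104 weeks before 100 deaths | 65 | 63 |

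If the HR is 1 in all arms, 100 deaths come at 28.2 or 25.6 months, so the gap widens. April 2014 to January 2017 is 33 months, which suits 100 deaths and is too short for the two-year rule at either rate.

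**4. How often deaths come first.** In 50,000 simulated trials with random accrual (100 deaths at 32.5 / 30.0 months), the share in which the last patient has under 104 weeks at the 100th death is, for 1.7/week / 10/month:
- plan inputs: 99% / 98%
- 0.0197/week (the larger historical trial's hazard): 96% / 89%
- 0.0197/week with an assumed 5% annual loss: 68% / 53%

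**5. Effect on operating characteristics.** The documents do not define the prior weight w, so I assume it is a number of events. The prior on log HR is treated as flat. The posteriors are then λ_T ~ Gamma(d_T, E_T) and λ_C ~ Gamma(w + d_C, w/0.0216 + E_C), where d is deaths and E is exposure. Success is P(λ_T < λ_C) > 0.84. Results are from 20,000 trials (log-rank 6,000).

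| Accrual, trigger | Strong prior | Weak prior | Log-rank |
|---|---|---|---|
| 1.7/week, 100 deaths | 81.5% | 74.8% | 73.0% |
| 1.7/week, 104 weeks | 83.5% | 77.4% | 75.4% |
| 10/month, 100 deaths | 81.3% | 75.1% | 73.5% |
| 10/month, 104 weeks | 83.3% | 76.9% | 74.2% |
| Stated in the plan | 83% | 74% | 73% |

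Bayesian type I error is 13–14% (strong) and 15–16% (weak) throughout. Schoenfeld's formula with 2:1 allocation and one-sided 0.14 gives 71.0% at 73.3 deaths in the two compared arms (100 in total) and 73.5% at 80.0 (1.7/week, two years). The stated strong-prior power sits nearer the two-year run and the stated weak-prior power nearer the 100-death run, so the powers do not show which trigger was simulated.

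**6. Interim narrative versus tables.** At 10/month, interim 2 falls at (32/2.30 + 12)/4.348 = 6.0 months and interim 3 at 17.9. Protocol 12.2.13 says about 6 and about 17 in the text, and 7.1 and 20.4 in the tables.

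**The case against.** The strongest reply is that 100 deaths plainly dominates. The completion definition names it as the final-analysis trigger, and the design summaries, the result tables and the synopsis agree. On this view the two-year sentence is leftover wording. That is probably how the trial would be run, and it is why removing the sentence is the simplest repair. But the sentence is the plan's formal statement of when the primary objective is met, it is backed by a simulation input, and both were carried into the SAP.

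A second reply is that two years of follow-up cannot be literal. By the plan's hazards only 60 × e^(−2.246) + 60 × e^(−1.498) ≈ 20 of 120 patients survive 104 weeks. This is correct, and it is why the check uses potential follow-up. On a literal reading the condition could never be met.

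A third is that about 100 deaths is simply the count expected at two years. The expected count there is 107 to 108, and 32.7 months is too early for the two-year rule at either rate.

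Three smaller points stand:
- The follow-up-until-death statements describe individual follow-up and do not set a cut-off. They need aligning but are not a third trigger.
- The interim 3 text (about 17 months) is close to the 10/month result (17.9) without matching it, so its origin is inferred. Text and table nevertheless count from the same first patient visit and differ by 3.4 months.
- For interim 2, the text counts from first randomization and the table from first patient visit, which may explain part of that gap.

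**Conclusion.** Both defects hold. The plan does not say which of its two triggers governs, and they fall about 6 to 7.5 months apart, deaths first. The conclusion rests on the plan's hazards and HRs, no loss to follow-up and the potential-follow-up reading. Slower deaths with some loss narrow the gap but still leave deaths first in more than half of simulated trials.

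The inferential cost is small: 1 to 3 points of power and essentially no change in type I error, conditional on the assumed meaning of the prior weight. The sample size is not at issue; the problem is an ambiguous cut-off for the primary decision. It should be fixed, though the trial does not fail on it.

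The accrual slip alone is minor. It changes no sample size, threshold or decision rule, and the tabulated timings are coherent at 1.7/week.

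**What to change.** - **State one cut-off** in Protocol 12.1 and SAP 5.2. The simplest is 100 deaths, with the two-year condition deleted. The alternative is the later of 100 deaths and 104 weeks after the last patient. That would require matching changes to the completion definition, Protocol 8.1, 8.1.1 and 10, SAP 5.1 and 6.5, SAP Table JBAS.6.1 and the synopsis calendar.
- **Check the existing FACTS final-analysis run** for the trigger it used. Restate final power, log-rank power and timing only if that differs from the trigger chosen.
- **Print one accrual rate**, either 7.4/month (1.7/week) or 10/month (2.3/week), and make the interim 2 and 3 text agree with their tables, counted from the same start point.

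The cost is mostly wording. If the run used the two-year rule and 100 deaths is kept, stated power may fall by about 2 points. If the two-year rule is kept, the timeline lengthens to 36–40 months. Keeping 1.7/week leaves the interim tables as they are. Choosing 10/month moves the tabulated 7.1, 20.4 and 32.7 months to about 6.0, 17.9 and 30.2, and the interim 2 futility probabilities would need rerunning because fewer deaths would have accrued by then.
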